3.5.4 Participant adherence monitoring

Study drug containers will be returned to study coordinators at the conclusion of each 2-week period during dose escalation (weeks 2, 4 and 6), and at the conclusion of each 4-week period during follow-up (weeks 10, 14 and 18). Pill counts will be performed to assess participant adherence with prescribed study drug.

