acceptance (defined as the patient reporting unwillingness to take the study drug). If one of these events occur, the participant will return to the prior tolerated oral furosemide dose. If one of these events occurs at the lowest administered dose, oral furosemide will be stopped and not re-started.

The window for each dose-titration period intervention/treatment visit is -4 to +4 days.

Follow-up (period 2)

Weeks 10 and 14: Participants who tolerated (i.e. no hypokalemia, serious hypotension, symptoms, etc.) and accepted furosemide in period will continue their maximally tolerated period 1 dose during the 12-weeks of follow-up. At weeks 10 and 14, they will receive additional 4-weeks supplies of this furosemide dose.

As specified in **Section 1.3.1**, if a participant has electrolyte abnormalities or other side effects attributable to furosemide in period 2 (i.e. on their period 1 maximally tolerated dose), the dose will be lowered sequentially (i.e. dose de-escalation: $160 \rightarrow 120 \rightarrow 80$ mg twice daily, or, if on alternative dosing due to prior diuretic use, decrease dose by 50%, rounded to the nearest whole tablet strength of existing (i.e. available) furosemide tablet formulations, until tolerated). If side effects persist or if the participant chooses, oral furosemide will be stopped.

Week 19: At the first weekly treatment (i.e. Monday or Tuesday) of study week 19, participants will return all unused study drug to a study coordinator.

The window for each follow-up period intervention/treatment visit is -4 to +4 days.

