4.4 Follow- up procedures (by visit types)

All study visits will occur at the time of routinely scheduled HD treatments at the patient's usual outpatient dialysis clinic. *Section 5* describes the measurements and assessments in detail.

Blood samples (weeks 1, 2, 3, 4, 5, 6, 10, 14, and 18): Blood will be obtained for the measurement of serum sodium, potassium, chloride, urea, creatinine, magnesium, calcium, albumin, and furosemide level. An additional 2.5 mL blood sample will be drawn, frozen, and stored in UNC Kidney Center -80° freezers for future testing as needed.

Urine samples (weeks -1, 5, 12, and 18): 24-hour urine collections will be obtained for the measurement of urine volume, sodium, urea, creatinine, and furosemide level. An aliquot of urine will be taken from the sample after the before-listed measurements are performed and be frozen and stored in UNC Kidney Center -80° freezers for future testing as needed.

Adherence assessments (weeks 1, 2, 3, 4, 5, 6, 8, 10, 12, 14, 16, and 18): Study staff will complete pill counts.

Acceptance assessments (weeks 1, 2, 3, 4, 5, 6, 8, 10, 12, 14, 16, and 18): Study staff will ask the participant the acceptance question.

Symptom assessments (weeks 1, 2, 3, 4, 5, 6, 8, 10, 12, 14, 16, and 18): Study staff will administer surveys evaluating patient-reported cramping, dizziness/pre-syncope, unusual tiredness/weakness, chest pain, rash, nausea, vomiting, diarrhea, tinnitus, hearing change, and numbness/tingling.

Hearing assessments (weeks 2, 4, 6, 10, 14, and 18): Study staff will administer the Inner EAR instrument.

Clinical data (weeks -4 to 18): HD treatment-level data (BPs, weights, dialysis prescription) will be obtained from the EHR.

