6.1 Primary Endpoints

Short-term and longer-term efficacy- urine volume (assessed separately)

- Among participants with baseline 24-hour urine volume ≥200 mL: incidence of ≥25% increase in urine volume
- Among participants with baseline 24-hour urine volume <200 mL: incidence of a ≥50 mL increase in urine volume to a urine volume of at least 100 mL/24-hours

Short-term and longer-term safety- electrolytes (assessed separately)

- Incidence of serum potassium <3.2 mEq/L
- Incidence of serum magnesium <0.8 mg/dL
- Incidence of serum corrected calcium <7.0 mg/dL

Short-term and longer-term safety- furosemide levels

• Incidence of serum furosemide level >12 microgram/L

Short-term and longer-term safety- BP

 Incidence of dialysis-associated hypotension requiring hospitalization or treatment in an emergency room and not attributable to overt sepsis, acute myocardial infarction, or other cardiovascular event (e.g. aortic dissection)²¹

Short-term and longer-term safety- symptoms (assessed separately)

- Incidence of severe or very severe patient-reported rash, tinnitus, or hearing change) not attributable to causes
 other than furosemide
- Incidence of 10-point decrease in Inner EAR instrument score

Short-term and longer-term tolerability- symptoms (assessed separately)

• Incidence of severe or very severe patient-reported cramping, dizziness/pre-syncope, unusual tiredness/weakness, chest pain, nausea, vomiting, or diarrhea not attributable to causes other than furosemide

Short-term and longer-term acceptability

• Incidence of an affirmative response to the furosemide acceptance question

Short term- and longer-term adherence

• Incidence of participants having <20% of furosemide pills remaining at pill counts

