6.2 Exploratory Endpoints

Short-term and longer-term efficacy- alternative definitions (assessed separately)

- Absolute change in urine volume from baseline (continuous in mL urine)
- Percentage change in urine volume from baseline (continuous in %)

Short-term and longer-term safety- electrolytes- alternative definitions (assessed separately)

- Absolute change in serum potassium from baseline (continuous in mEq/L)
- Absolute change in serum magnesium from baseline (continuous in mg/dL)
- Absolute change in serum corrected calcium from baseline (continuous in mg/dL)
- Percentage change in serum potassium from baseline (continuous in %)
- Percentage change in serum magnesium from baseline (continuous in %)
- Percentage change in serum corrected calcium from baseline (continuous in %)

Short-term and longer-term safety- BP- alternative definitions (assessed separately)

- Incidence of intradialytic systolic BP <80 mmHg²¹
- Incidence of intradialytic systolic BP <90 mmHg⁴¹
- Lowest systolic BP during HD (continuous in mmHg)

Short-term and longer-term acceptability alternative definitions (assessed separately)

- Number (percentage) of participants withdrawing from the study
- Number (percentage) period 1 participants not continuing to period 2

Short-term and longer-term adherence alternative definitions (assessed separately)

- Number (percentage) of furosemide tablets not taken (# tablets remaining/# tablets provided)
- Serum furosemide level (continuous in microgram/L and binary, present vs. absent)
- Urine furosemide level (continuous in microgram/L and binary, present vs. absent)

Clinical endpoints (assessed separately)

- Change in 24-hour creatinine clearance from baseline (continuous in ml/min/1.73m²)
- Percentage change in 24-hour creatinine clearance from baseline (continuous in %)
- Change in 24-hour fractional excretion of sodium from baseline (continuous in %)

- Change in 24-hour fractional excretion of urea from baseline (continuous in %)
- Percentage change in 24-hour fractional excretion of urea from baseline (continuous in %)
- Pre-HD systolic BP (mmHg on a per-HD treatment basis)
- IDWG (kg on a per-HD treatment basis)
- UF volume (mL on a per-HD treatment basis)
- UF rate (mL/h/kg on a per-HD treatment basis)
- Target weight achievement (post-HD weight (kg) within 1kg of prescribed target weight) (binary on a per-HD treatment basis)

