6.3.4 Primary analyses (each assessed separately)

At designated study time-points, we will determine the [data type; see **Section 6.1** for definitions]:

- change from baseline for the short and longer-term efficacy measure [binary] (24-hour urine volume);
- value of short and longer-term safety electrolyte measures [binary] (serum potassium, magnesium, corrected calcium);

- value of serum furosemide levels [binary] (short and longer-term safety furosemide level measure);
- incidence of dialysis-associated hypotension [binary] (short and longer-term safety blood pressure);
- incidence of severe or very severe patient-reported allergic or toxicity-related symptoms [binary] (short and longer-term safety symptom measures);
- change from baseline of Inner EAR instrument score [binary] (short and longer-term safety symptom measure);
- incidence of severe or very severe patient reported symptoms [binary] (short and longer-term tolerability symptom measures);
- incidence of patient-reported acceptance of furosemide [binary] (short and longer-term acceptability measure);
- incidence of adherence by pill counts [binary] (short and longer-term adherence measure).

Change measures and value measures (e.g. 24-hour urine volume, serum electrolytes, serum furosemide level) will be analyzed via one-way repeated measures of analysis of variance to determine the presence of absence of dose-related differences. In addition, we will use mixed effects modeling to test the effect of increased dose and duration with the fixed effect of time (dose), random subject effect, and an unstructured repeated covariance type. We will use generalized estimating equations to assess categorical outcomes (e.g. sufficient increase in 24-h urine volume, hypokalemia, hypomagnesemia, hypotension, symptoms, Inner EAR score, patient acceptance). We will also consider binary outcomes as rates (events/time).

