6.3.7 Sensitivity analyses

We will conduct sensitivity analyses to test the robustness of our findings. Results of these analyses will be used to guide soundness of the main results. If the main results are demonstrated to be fragile, we will soften our conclusions around the main results as appropriate. Alternatively, if the main results are demonstrated to be robust, we will be confident in our main results conclusions. Specifically, we will conduct sensitivity analyses:

- excluding data from participants with endpoints drawn "off-schedule" (e.g. serum electrolytes, 24-hour urine, symptom assessment, etc.);
- excluding data with questionable values;
- testing for difference by clinic;
- evaluating the impact of variations on model assumptions and covariates;
- evaluating model residuals;
- testing for difference with transformations of scale and changes in the definitions of outcome variables

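### The primary adherence endpoint takes no account of days since dispensing and does not name the counts that are scored; separately, the plan leaves drug supply for the week 18 urine unsettled

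*Combined protocol and SAP*

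**What the plan says.** Section 6.1 of the combined protocol and SAP gives one primary adherence endpoint for both periods: "Incidence of participants having <20% of furosemide pills remaining at pill counts". Section 6.3.4 carries it into the analysis as "incidence of adherence by pill counts [binary] (short and longer-term adherence measure". Neither section names the counts to be scored, says whether kits are pooled within a period, or relates tablets left to the time since they were handed out. A denominator appears only in the exploratory version in Section 6.2, "Number (percentage) of furosemide tablets not taken (# tablets remaining/# tablets provided", which also has no time term.

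Section 4.4 schedules twelve on-treatment counts: "Adherence assessments (weeks 1, 2, 3, 4, 5, 6, 8, 10, 12, 14, 16, and 18): Study staff will complete pill counts". Section 3.5.4 links adherence to the return of containers: "Study drug containers will be returned to study coordinators at the conclusion of each 2-week period during dose escalation (weeks 2, 4 and 6", and in period 2 "at the conclusion of each 4-week period during follow-up (weeks 10, 14 and 18". Section 3.5.11 likewise has the leftover tablets counted when a container comes back at the end of its period. Section 3.5.3 sets kits at two weeks' supply in period 1 and four weeks' in period 2, and mentions no spare tablets. Section 4.3 adds: "The window for each dose-titration period intervention/treatment visit is -4 to +4 days", with the same window in period 2.

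On the end of supply, Section 3.5.3 and the visit tables (Table 2) place the last dispensing, of a four-week supply, at week 14. Section 4.1 puts the final 24-hour urine at the mid-week session of week 18. Section 3.5.4 returns containers at week 18, whereas 4.1 and 4.3 return unused drug at week 19. The opening paragraph of 4.3 also lists a week 18 drug visit that does not appear in 3.5.3 or Table 2.

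**The concern.** A fixed cut-off on tablets left measures adherence only if every kit is counted after the same number of days. If a visit moves, the same behaviour gives a different score. An early count makes a fully adherent participant look non-adherent. A late count can pass someone who missed many doses or ran out. Adherence is a primary endpoint of this pilot, so its rate should reflect tablets taken and not the calendar.

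The week 18 urine is one of only two follow-up collections (weeks 12 and 18) that can inform longer-term efficacy. Section 1.2 gives a diuretic effect of 6 to 8 hours. A collection made after tablets ran out would measure urine volume off drug.

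**Working it through.** **Inputs.** Cut-off 20% left (6.1); denominator tablets provided (6.2); kits of K = 14 or 28 days (3.5.3); two doses a day (3.5.2); visit window of 4 days either way (4.3). Assumed: no spare tablets, and sessions on Monday/Wednesday/Friday or Tuesday/Thursday/Saturday. A first-of-week visit can then fall 3 days early, on time, or 2 or 4 days late.

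**Formulas.** With d days from dispensing to count:
- share left after perfect adherence = (K − d)/K, or 0 once d reaches K;
- pass mark as a share of calendar doses due = 0.8 × K/d.

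**The plan's own figure.** K = 14, d = 14: 0.8 × 14/14 = 80%. The rule does what it intends when visits are on time.

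**Scored per kit at container return, one visit moved:**

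| Kit | Days elapsed | Left if perfect | Pass mark |
|---|---|---|---|
| 14 d | 10 | 4/14 = 28.6%, fails | 112.0% |
| 14 d | 11 | 3/14 = 21.4%, borderline | 101.8% |
| 14 d | 14 | 0%, passes | 80.0% |
| 14 d | 18 | 0%, passes | 62.2% |
| 28 d | 24 | 4/28 = 14.3%, passes | 93.3% |
| 28 d | 25 | 3/28 = 10.7%, passes | 89.6% |
| 28 d | 28 | 0%, passes | 80.0% |
| 28 d | 32 | 0%, passes | 70.0% |

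A single visit moved 4 days late produces both period 1 extremes: it closes an 18-day interval and opens a 10-day one.

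**The 10- and 11-day counts in doses.** A 14-day kit holds 28 doses. At 11 days, 22 doses taken leaves 6/28 = 21.4% (fail). If that morning's dose was taken before the count, 23 taken leaves 5/28 = 17.9% (pass). At 10 days, 20 or 21 taken leaves 8/28 = 28.6% or 7/28 = 25.0%, and both fail.

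**The 18-day count.** The kit is empty after day 14 if taken as directed, so the most anyone can take is 14/18 = 77.8% of calendar doses. Against tablets actually supplied, the pass mark is still 80%.

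**Pooled over period 1.** With 42 days of tablets and one moved visit, a perfect adherer has at most 4/42 = 9.5% left and passes. If only the last visit moves by the full window, the pass mark runs from 33.6/46 = 73.0% to 33.6/38 = 88.4%.

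**Mid-kit counts.** Weeks 1, 3, 5, 8, 12 and 16 fall half-way through a kit: (14 − 7)/14 = 50% and (28 − 14)/28 = 50% left. Every perfect adherer would fail if these were scored.

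**Week 18 urine.** Take the on-time week 14 visit as day 0, with the first dose that day. A 28-day kit covers days 0 to 27. The first session of week 18 is day 28 and the mid-week session is day 30. A 24-hour collection begun the day before starts on day 29, and 29 − 27 = 2 days after the last covered day. This assumes no spare or missed tablets and no week 18 supply.

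**The case against.** The strongest defence is that the intended reading is benign. Sections 3.5.4 and 3.5.11 tie adherence counting to returned containers, and a rule that no perfect adherer could pass at mid-kit cannot have been meant. This stands. A reader might infer from 4.4 that perfect adherers will be failed at half of all counts, but no section says mid-kit counts are judged against the 20% rule. What remains is an ambiguity: 6.1 does not say which counts it means, and the repeated-measures method in 6.3.4 leaves room for scoring each one.

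A reader might also take the pass mark to swing freely between 62% and 112%. That is a per-kit figure for period 1 only. The low end counts days without tablets as due, and pooling the period removes the failure. The endpoint is worded per participant and Section 6 measures short-term endpoints over the six weeks, so pooling is a fair reading. The plan does not choose it.

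Other measures soften the problem. Serum and urine furosemide levels are separate adherence measures, and the accountability logs in 3.5.8 and 3.5.10 probably allow elapsed days to be recovered. Section 6.3.7 plans changes to outcome definitions among its sensitivity analyses. However, it specifies no time-scaled adherence score, and its item on "excluding data from participants with endpoints drawn" off schedule removes data and does not rescale counts taken inside the window. No dose decision or stopping rule depends on the score, and this is a single-arm pilot focused on estimates.

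On the week 18 urine, the week 18 drug visit in 4.3 and the week 19 return suggest that dosing was meant to continue. That is a fair reply to any claim that the urine is collected off drug, but it does not settle where the tablets come from.

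**Conclusion.** The point holds in a limited form. Scored per kit at container return, the rule fails a perfect adherer whose 14-day kit is counted at 10 days, is borderline at 11 days, and at 18 days passes anyone above 62% of calendar doses. In period 2 no single moved visit fails a perfect adherer, and pooled over period 1 none does. These results assume the Section 6.2 denominator, no spare tablets and the session days stated above. The documents do not give the frequency of moved visits, so neither the size nor the net direction of the effect on the adherence rate can be stated.

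For the week 18 urine, following 3.5.3 and Table 2 to the letter leaves a gap of about 2 days. A reader might conclude that the longer-term efficacy result will be measured off drug. The documents do not support that, because 4.1 and 4.3 point the other way. The finding is an unresolved inconsistency that touches a primary efficacy endpoint.

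Both matters should be corrected because correction is cheap. Neither undermines the study as a whole.

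**What to change.** - **Score.** Define adherence as tablets taken divided by tablets due from dispensing to the count, with tablets due capped at tablets supplied. Keep the 80% cut-off. A perfect adherer then scores 20/20 doses at 10 days, and 28/28 at 18 days instead of 28/36 = 77.8%.
- **Counts.** State in 6.1 that container-return counts are the scored ones, and whether the score is per kit or pooled over the period. Take dispensing dates from the accountability log, and record whether that day's dose preceded the count.
- **Limit of the cap.** It repairs early counts. A late count of a kit without spares is still judged on tablets supplied. About four spare days per period 1 kit would address that, but only with the new denominator: under the present rule an on-time perfect adherer would have 4/18 = 22.2% left and fail.
- **Week 18 urine.** Give enough tablets at week 14, or a week 18 top-up, to last until the collection is complete. With an on-time week 14 visit, days 0 to 30 need 31 days' supply; a visit 4 days early needs 35. Use the new denominator here too, since 7/35 = 20% left at an on-time count would fail the present rule.
- **Consistency.** Align 3.5.3, 3.5.4, 4.1 and 4.3 on the last dispensing visit and on when drug is returned, so that tablets are not collected before the urine.

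The cost is protocol wording, a few extra tablets and slightly more analysis work.

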6.2 Exploratory Endpoints

Short-term and longer-term efficacy- alternative definitions (assessed separately)

- Absolute change in urine volume from baseline (continuous in mL urine)
- Percentage change in urine volume from baseline (continuous in %)

Short-term and longer-term safety- electrolytes- alternative definitions (assessed separately)

- Absolute change in serum potassium from baseline (continuous in mEq/L)
- Absolute change in serum magnesium from baseline (continuous in mg/dL)
- Absolute change in serum corrected calcium from baseline (continuous in mg/dL)
- Percentage change in serum potassium from baseline (continuous in %)
- Percentage change in serum magnesium from baseline (continuous in %)
- Percentage change in serum corrected calcium from baseline (continuous in %)

Short-term and longer-term safety- BP- alternative definitions (assessed separately)

- Incidence of intradialytic systolic BP <80 mmHg²¹
- Incidence of intradialytic systolic BP <90 mmHg⁴¹
- Lowest systolic BP during HD (continuous in mmHg)

Short-term and longer-term acceptability alternative definitions (assessed separately)

- Number (percentage) of participants withdrawing from the study
- Number (percentage) period 1 participants not continuing to period 2

Short-term and longer-term adherence alternative definitions (assessed separately)

- Number (percentage) of furosemide tablets not taken (# tablets remaining/# tablets provided)
- Serum furosemide level (continuous in microgram/L and binary, present vs. absent)
- Urine furosemide level (continuous in microgram/L and binary, present vs. absent)

Clinical endpoints (assessed separately)

- Change in 24-hour creatinine clearance from baseline (continuous in ml/min/1.73m²)
- Percentage change in 24-hour creatinine clearance from baseline (continuous in %)
- Change in 24-hour fractional excretion of sodium from baseline (continuous in %)

- Change in 24-hour fractional excretion of urea from baseline (continuous in %)
- Percentage change in 24-hour fractional excretion of urea from baseline (continuous in %)
- Pre-HD systolic BP (mmHg on a per-HD treatment basis)
- IDWG (kg on a per-HD treatment basis)
- UF volume (mL on a per-HD treatment basis)
- UF rate (mL/h/kg on a per-HD treatment basis)
- Target weight achievement (post-HD weight (kg) within 1kg of prescribed target weight) (binary on a per-HD treatment basis)
- Post-HD weight- target weight difference (post-HD weight prescribed dry/target weight, kg on a per-HD treatment basis)
- Extra HD treatments (number)
- Hospitalizations (number)

